## **STATEMENT OF COMPLIANCE**

This document is a protocol for a clinical trial. The study will be conducted in compliance with all stipulations of this protocol, the conditions of ethics committee approval, the NHMRC National Statement on Ethical Conduct in Human Research (2007) and the Note for Guidance on Good Clinical Practice (CPMP/ICH-135/95).

## PROTOCOL SYNOPSIS

Title	Safety study of sibling cord blood cell infusion to children with cerebral palsy
Objectives	
The primary objective of this study is to gain preliminary information on the safety of 12/12 HLA matched umbilical cord blood cell (UCBC) infusion in children with cerebral palsy (CP).
 
The secondary objectives of this study are:
 

A) to gain preliminary information on the treatment effect of 12/12 HLA matched UCBC infusion

B) to better understand the length of time that infused matched sibling UCBCs remain within recipients

C) to gather information and samples for future studies into mechanistic activity of UCBCs

Trial sites	
The Royal Children's Hospital Melbourne Lady Cilento Children's Hospital Brisbane The Children's Hospital at Westmead (recruitment) Monash Health (recruitment)

Participants	
Number to be enrolled for screening: 48 Number to continue through trial: 12; Age: 1 - 16 years old

**GLOSSARY OF ABBREVIATIONS**

ABBREVIATION	TERM
AusCord	Australian National Network of Umbilical Cord Blood Banks and Cord Blood Collection Centres
ABMDR	Australian Bone Marrow Donor Registry
ABMTRR	Australasian Bone Marrow Transplant Recipient Registry
AE	Adverse event
BMDI CBB	BMDI Cord Blood Bank
BMI	Body mass index
CBB	Cord blood bank
CBU	Cord blood unit
CHW	The Children's Hospital at Westmead
CIBMTR	Center for International Blood & Marrow Transplant Research
CP	Cerebral palsy
DMSO	Dimethyl sulfoxide
EPO	Erythropoietin
GMFCS	Gross motor function classification system
GvHD	Graft-versus-host disease
HLA	Human leucocyte antigen
LCCH	Lady Cilento Children's Hospital Brisbane
MCRI	Murdoch Children's Research Institute
MNC	Mononuclear cells
MRI	Magnetic resonance imaging
NSW CPR	New South Wales Cerebral Palsy Register
OT	Occupational therapy
PT	Physiotherapy
PVC	Peripheral venous catheter
QCPR	Queensland Cerebral Palsy Register
RCH, Melbourne	The Royal Children's Hospital Melbourne
RCT	Randomised controlled trial
SAE	Serious adverse event
SCBB	Sydney Cord Blood Bank
SOP	Standard operating procedure
TNC	Total nucleated cells
TRECs	T-cell receptor excision circles
UCB	Umbilical cord blood
UCBCs	Umbilical cord blood cells
VCPR	Victorian Cerebral Palsy Register

### 1.2. Study management

The study will be managed by a research team consisting of principal investigators, associate investigators and clinical trial coordinators who will manage the daily operations such as recruitment, follow up assessments and study documentation. This is a multisite clinical trial, and each site will be managed by a different Principal Investigator. Across the sites, there will be a number of teams for different aspects of the trial, each with a designated team leader (please see below).

This trial is investigator-initiated by a collaborative research group. This trial does not have a sponsor.

#### Principal Investigators

Principal Investigators at each site will coordinate the supporting departments within the hospital. They will undertake site meetings and have access to a clinical trial coordinator working in each state.

### *Infusion*

The infusion team will be headed by [name], paediatric transplant physician at the RCH Melbourne. [name], LCCH Brisbane and by [name], paediatric transfusion medicine specialist, RCH Melbourne. Once the trial is underway, the steering committee will consider expanding the trial to include a third infusion site hospital, in NSW, to further demonstrate the feasibility of this trial as a multi-site project.

### Therapy

All participants will receive their regular rehabilitation therapy.

### Assessment

Safety assessment will primarily be conducted by both the infusion team (described above). Therapists and a psychologist independent of the therapy team providing rehabilitation, and laboratory staff, will complete other components of the safety assessment as well as assessments relative to secondary aims of the study. The team will undertake structured training in assessment tools prior to trial commencement.

### Safety and Data Monitoring Committee

This committee will meet every three months, including after the first three participants have reached one month post-infusion for review prior to further participant infusions.

[name], paediatric oncologist (Chair)  
[name], statistician  
A/[name], paediatric rehabilitation specialist  
[name], paediatric transplant specialist  
[name], developmental paediatrician

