### 4. STUDY DESIGN

This is a multi-site safety study.

Sibling donor UCBCs require careful DNA testing to ensure matching with the recipient (participant). Only about 25% of siblings have full-matched blood, the 75% that are not full-matched will be excluded. No immunosuppression will be used, as the infused cells do not need to survive for long periods within the recipient and immunosuppression increases the safety risk. The first six enrolled participants to receive infusions will be GMFCS IV or V; participants with mild or moderate CP (GMFCS I, II or III) will be waitlisted. This is because the safety profile of matched sibling UCBC infusion for children with CP is unknown, we feel it is more ethical to initially trial in the participants with severe CP and gather information for interim Data Safety Monitoring Committee (DSMC) review, before continuing the trial with less impaired participants. The DSMC will review safety data from the first three participants after three months post-infusion and decide whether the trial can progress to the next three participants. After these initial six participant infusions, the DSMC will decide whether the trial can progress to infusions of participants with mild CP or not. The DSMC will provide a report to the Trial Steering Committee, who will provide the report directly to the RCH HREC for review. The HREC will make a final decision about whether the trial can expand to include children with mild or moderate CP at this point, or whether the trial will remain restricted to children with severe CP only.

[figure not shown]

Figure 1: Participant timelines for the study

Figure 2: Recruitment decision making process (next page)

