#### 4.2. Expected duration of study

The study is expected to take 2 years until final follow up and data analysis. This allows recruitment and screening over three months, then sequential treatment in groups of three. Each group of three is expected to be treated within one month, then followed until three months post-infusion for Data Safety Monitoring Committee (DSMC) review and approval to continue. After the first two groups of three, the final six participants will be infused. The final 12 month follow up assessment for each participant will occur 13 months after baseline measurements for each individual.

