#### 4.3. Primary and secondary outcome measures

The primary objective of this study is to collect initial safety data during and after infusion of sibling UCBCs. The following outcomes will be collected to assess this objective which will be assessed at three time points:

- 1) During the infusion and up to 36 hours after
  - Clinical assessment, including vital signs and pulse oximetry
  - Laboratory assessment looking for markers of infection

- Occurrence of AEs and SAEs
- 2) Within the three months after infusion
  - Clinical assessment
  - Laboratory assessment looking for markers of immune reaction
  - Deterioration of motor function as assessed by Gross Motor Function Measure
  - Occurrence of AEs and SAEs
- 3) Within the 12 months after infusion
  - Clinical assessment
  - Deterioration of motor or cognitive function as assessed by the appropriate tool (see section 7.3)
  - Occurrence of AEs and SAEs

The secondary outcomes include:

- Efficacy of the intervention at 3 months measured by therapists on a suite of standardised psychometrically sound measures of movement, cognition and quality of life. This will be assessed in an exploratory fashion only. The areas for assessment were selected to focus on motor outcomes because CP is a primarily motor disorder; on cognitive outcomes that have shown change in an international trial [49] and anecdotally from private stem cell clinics (changes in wakefulness, attentiveness and alertness have been described); and how these might affect the participant's life; The motor and quality of life outcomes will also be measured at 3 months. Cognition will be measured at 12 months after infusion and used to calculate change from baseline. Again, the analysis of the 12 month data will be exploratory in nature.
- Understanding the longevity of infused cells. This will be achieved using chimerism studies (engraftment analysis), looking for infused cells circulating in a sibling recipient's blood. We will study chimerism by extracting circulating cell free DNA from plasma and using a new quantitative PCR method detecting differences in copy number deletions between the recipient and donor. It will be reported as the fraction of donor DNA in the sample at each time point for each individual, and constitutes both a safety and mechanistic study.

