All participants will be observed carefully by the nurse following the infusion (see section 7) with a transplant physician available if observations fall outside the normal range (see section 8). Blood will be collected by the nurse 1 hour after conclusion of infusion to compare with baseline.

Participants will be released from the hospital if they are haemodynamically stable and do not have haemoglobinuria. Participants will return to the hospital the next day for a physical examination and blood test. If there is any indication of infection or serious adverse event, the participant may need to remain in hospital for observation or medical attention. This is not expected. Participants will be provided with emergency phone numbers and instructions (see Appendix 11: Post-infusion handout).

Further blood samples will be taken at 1 week, 1 month and 3 months, for both research and safety reasons (see Table 1).

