## 6. STUDY VISITS AND PROCEDURES SCHEDULE

Study phase	Enrolment	Baseline	Infusion	Follow up					
Visit number	1	2	3	4	5	6	7	8	9
Timing	> 8 wks prior to infusion	21 days prior to infusion	0	1 day	1 wk	1 mo	3 mo	6 mo	12 mo
Tolerance	Any time	> 3 wks since Visit 1	- Within 10-30 days of clear virology screen - CBU available	± 0 days	±2 days	± 7 days	± 2 wks	± 2 wks	± 2 wks
Location	Hospital	Hospital	Hospital	Hospital	Hospital, home	Hospital	Hospital	Hospital, community	Hospital
Informed consent (45 mins)	X								
CP assessment (30 mins)		X							
Medical history (0.5 hr)		X							
Physical examination (0.5 hr)		X	X	X		X	X	X	X
Medical assessment (10 mins)				X	X	weekly	X	X	X
Assessment of motor function (45 mins)		X					X		X
Assessment of upper limbs (15 mins)		X					X		X
Assessment of quality of life (0.5 hr)		X					X		X
Assessment of cognition (2hr 15)		X							X
Infusion of UCB (30 mins)			X						
Intravenous fluids, observation (6 hrs)			X						
Anti-D administration if required (5 mins)				X					
Blood collection	X	X	2X	X	X	X	X		
Rehabilitation Therapy									
Length of visit	1 hr	6 hrs (may need two visits)	9 hrs	1 hr	1 hr	1 hr	2 hrs	1 hr	4 hrs

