#### Motor assessment (baseline and at visits 7 and 9)

The gold standard gross motor measure for CP, the Gross Motor Function Measure (GMFM-66) will be used. The GMFM-66 has good validity and reliability, and is the only gross motor measure responsive to change for children [59]. The assessment can be scored from videotape if needed. 45 mins to complete (participant)

An upper limb assessment will also be used, the Quality of Upper Extremity Skills Test (QUEST). This tool is validated for use with children aged 18 months to 8 years and has been used in the older range needed for this study [60]. Results will be reported for each limb separately. This tool is reliable and sensitive to change, but has the disadvantage that it measures impairment reduction rather than functional improvement. The QUEST can be scored from videotape if needed. 15 mins to administer (participant)

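### Section 1.3 sets the safety review of the first three children at one month post-infusion, while Sections 4 and 4.2 set the same go/no-go review at three months

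*Protocol*

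**What the plan says.** Three places in the protocol time the review of the first three infused children.

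- Section 1.3, under the Safety and Data Monitoring Committee, says the committee meets every three months, "including after the first three participants have reached one month post-infusion for review prior to further participant infusions".
- Section 4: "The DSMC will review safety data from the first three participants after three months post-infusion". The committee then decides whether the next three may proceed.
- Section 4.2: "Each group of three is expected to be treated within one month, then followed until three months post-infusion", at which point the committee reviews and must approve continuation.

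Section 4.3 defines three primary safety periods. The second is headed "Within the three months after infusion" and includes "Deterioration of motor function as assessed by Gross Motor Function Measure". On blood sampling, Section 5.5 says: "Further blood samples will be taken at 1 week, 1 month and 3 months, for both research and safety reasons". The Section 6 schedule and Section 7.3 place the first motor reassessment after baseline at Visit 7, three months after infusion.

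**The concern.** The texts concern the same three children and the same decision, namely whether more children may be infused. The committee's name varies slightly between sections, but the protocol describes only one such body. No text describes two successive reviews of the first group, and none says which section prevails.

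Section 1.3 is the committee's own section. A committee working from it could review at one month, allow further infusions and believe that it had followed the protocol. Section 4 gives the reason for staging: the safety profile of this infusion in children with cerebral palsy is unknown. At stake at this gate is the exposure of the next three children up to two months earlier than the design sections intend, without the three-month data that the plan collects for this purpose.

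**Working it through.** **Inputs**

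- Gate in Section 1.3: 1 month. Gate in Sections 4 and 4.2: 3 months.
- Time to infuse a group of three: within 1 month (Section 4.2, stated as an expectation).
- Visit 6: 1 month, tolerance 7 days either way. Visit 7: 3 months, tolerance 2 weeks either way (Section 6).
- Post-infusion blood samples due by three months: 4 hours, 24 hours, 1 week, 1 month, 3 months, so 5 (Table 1).

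**Difference between the texts**

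3 − 1 = 2 months.

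**Follow-up available at a one-month review**

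Take the review on the day the third child reaches one month.

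- Third child: 1 month of follow-up.
- First child: at most 1 + 1 = 2 months.
- Unobserved part of the three-month window: from 3 − 2 = 1 month to 3 − 1 = 2 months per child.

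**Visit 7 data**

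- Earliest permitted Visit 7: 3 months − 2 weeks, about 2.5 months.
- Longest follow-up at the review: 2 months.
- 2 < 2.5, so 0 of 3 children can have the 3-month blood and chimerism sample or the repeat GMFM.
- The first child could have reached Visit 7 only if the group took more than about 2.5 − 1 = 1.5 months to infuse. The third child could not have reached it in any case.

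**Blood samples**

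Nominally 4 of the 5 are due by one month. Because Visit 6 may fall up to 7 days late, a child at exactly one month may have only 3 of 5.

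**What a one-month review would miss**

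- The close of the second primary safety period in Section 4.3.
- The only motor reassessment that falls in that period.
- The 3-month sample for chimerism, inflammatory markers and signs of GvHD, and the 3-month examination by the transplant specialist (Section 7.1).
- The data for the slow-rejection category, which Section 9 defines at three months.

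**Does the stated duration show which interval was meant?**

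Section 4.2 gives 2 years until final follow-up and data analysis. Total = recruitment 3 + (1 + gate) + (1 + gate) + final six + 12 months of follow-up. The protocol gives no time for infusing the final six, so 1 to 2 months is assumed.

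| First gate | Second gate | Total |
|---|---|---|
| 3 months | 3 months | 24 to 25 months |
| 1 month | 3 months | 22 to 23 months |
| 1 month | 1 month | 20 to 21 months |

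Three-month gates come close to 24 months, but the sum allows nothing for analysis or for committee and ethics decisions. The shorter totals leave room for those steps. The duration does not settle the question.

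**The case against.** The best reply is that Section 1.3 is a committee listing and does not set a decision rule. It speaks of review and uses no word for decision or approval. To have reached one month is a minimum, and the same sentence has the committee meeting every three months. The decision rule sits in Sections 4 and 4.2, which agree. This stands in part: a three-month review breaches nothing, and harm arises only if someone follows Section 1.3 without the design sections. But Section 1.3 does place its review before further infusions, so it reads as a release point and should not carry a different interval.

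A second reply is that a one-month review would still be informed. That is correct. The weekly medical assessments, the samples to one week and, subject to its tolerance, the 1-month sample would exist. Under Section 8, GvHD of Grade II or above stops the trial at any time. What is missing is the material due between one and three months.

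A reader might infer three further faults, which the documents do not support.

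- That the six-month infusion stagger in Section 4.1 cannot hold two three-month gates. The follow-ups alone take 2 × 3 = 6 months, but each infusion is a single-day visit and one month per group is an upper limit. Infusions at about months 0, 3 and 6 just fit. A longer span of 9 to 10 months, from 2 × (1 + 3) + 1 to 2, needs a full month per group and the assumed time for the final six.
- That Section 4.4 sets a different second gate by tying it to all severe participants. Section 4 makes the first six infused children GMFCS IV or V and waitlists the others, so this reads naturally as shorthand for those six.
- That the two-year duration confirms three-month gates. The working shows that it does not.

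**Conclusion.** The inconsistency is real and lies in a conduct rule of the current protocol. One gate has two intervals, two months apart. On the shorter one, further infusions could be released with 0 of 3 children having Visit 7 data and with 1 to 2 months of each child's three-month safety window unobserved. These figures assume that the group is infused within one month, as Section 4.2 expects, and that the review takes place as soon as the third child reaches one month.

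The finding is limited. The protocol does not require release at one month, and the two design sections already agree on three. It is a wording fault that should be corrected because it governs exposure of children to an infusion of unknown safety. It does not show that the staging itself is unsound.

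**What to change.** In Section 1.3, change the review point for the first three participants from one month to three months post-infusion, to match Sections 4 and 4.2.

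Optionally, have the review wording in Section 4.4 and the six-month stagger in Section 4.1 refer to the sequence in Section 4.2. No new infusion-period figure should be written in, and the amendment should not claim that the two-year duration has been confirmed.

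The cost is one phrase in a protocol amendment. The second group would wait up to two months longer than Section 1.3 alone allows, and no longer than Sections 4 and 4.2 already require. If the investigators also want an early look at one month, Section 1.3 can keep it as an additional review that does not release further infusions.

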## 1.4. Funding and resources

---

Source	Funding / Resource
Research Foundation of the Cerebral Palsy Alliance	In kind; Cash

---

Cell Care Australia  
All other participating institutions

In kind; Cash  
In kind

## 2. INTRODUCTION AND BACKGROUND

### 2.1. Background information

Cerebral palsy (CP) describes a group of permanent non-progressive motor and postural disorders arising from damage to the developing brain while *in utero*, during birth or in the first years of life [1, 2], and affects around 2 per 1000 live births across the world. The main types of CP include spasticity (stiffness of muscles accounting for around 80% of all diagnoses), dyskinesia (abnormal involuntary movements) and ataxia (unsteadiness) which result from lack of normal nervous control of muscles. Depending on the location and severity of brain damage, different regions of the body may be affected. This is described as hemiplegia (one side of the body), diplegia (legs greater than arms) or quadriplegia (all limbs). The degree of motor impairment is often described using the Gross Motor Function Classification System (GMFCS), with GMFCS I indicating an otherwise normal child who may have impaired speed, balance or coordination, increasing in severity to GMFCS V indicating limited motor function, wheelchair use with limited head control. CP is often associated with epilepsy, difficulties in speech, sight, hearing, sensation, perception, behaviour or cognition. There is currently no cure for CP.

#### Scientific rationale

Recent interest in stem cell therapy for intractable neurological disorders has led to a large number of preclinical studies of brain injuries related to CP that show evidence of therapeutic potential. In particular, a greater understanding of the varied stem cells to be found in human umbilical cord blood (UCB), which is less ethically complicated than many other sources of stem cells, has led to a focus on UCB stem cell therapy. The stem cells in UCB do not form cancers and present a lower risk of graft-versus-host disease (GvHD) than bone marrow stem cells [3]. Transplantation of UCB cells in acute animal models of CP such as excitotoxic white matter injury [4] and neonatal hypoxia-ischaemia [5-10] have shown significant neurofunctional improvement, as have models of adult stroke [11-16], spinal cord injury [17-21] and traumatic brain injury [22]. On the other hand, preclinical studies showing no benefit from UCB cell (UCBC) treatment of acute brain injury have also emerged [23-25]. While some studies involve transplanting UCBCs directly to the injured area of the brain, there is strong evidence that the minimally invasive intravenous infusion to the periphery is equally as effective [4, 26]. Investigations into the mechanism of UCBC transplantation action reveal anti-inflammatory properties, protection of neural cells from secondary cell death, promotion of host cell proliferation and migration, and angiogenesis. It does not appear that human (xenogeneic) stem cells engraft to replace lost brain cells in immune-suppressed animal models. Thus the stem cell treatment is not considered a transplant but can be thought of as a transfusion.

The transfusion mechanisms described above are appropriate for the acute phase of brain injury, which involves inflammation, primary and secondary cell death and chemical signalling. Preclinical work has almost entirely focussed on acute brain injury, and it is unknown if these mechanisms will operate in the same way in the chronic phase of disease. This area has been well reviewed in the literature [27-31]. CP is a heterogeneous condition with varied brain pathology, so it is possible that stem cell infusion may act through different mechanisms for different children. For example, some children have large brain lesions that might benefit from increasing the number of available neurons, whereas there is evidence that some infants born preterm may have reduced number of neural connections rather than reduced number of neurons [32]. Improvement in functioning for children with the former pathology may be due to recruitment of endogenous stem cells caused by UCBC infusion [33]. The latter pathology may potentially be linked to increasing synapses and dendritic arborisation rather than generating new neurons from either infused or endogenous stem cells [34]. Recruiting endogenous stem cells would take time to replicate, differentiate, migrate and integrate new cells, while generating new synapses from existing neurons *in situ* could occur sooner.

